Study Protocol with Statistical Analysis Plan

Study Title: Post-operative Pain Control with Sphenopalatine Ganglion Nerve Block in
Septorhinoplasty Patients

NCT05667324

University of Florida Protocol ID: IRB202201279-A

Approved protocol date: 3/28/2023

IRB Protocol

1. Project Title: Post-operative pain control with sphenopalatine ganglion nerve block in septorhinoplasty patients

2. Investigator(s):

Principal Investigator: [name]

Co-Investigators:

[name]

[name]

[name] [name], DDS

[name], PHD

Study Coordinator: [name], PHD

Co-study coordinator: [name], CCRC

Other (faculty only listed):

[name]

[name]

[name]

[name]

[name]

[name], MS

[name]

[name]

[name]

[name]

3. Abstract:

Nasal septoplasty is a very common procedure performed by both otolaryngology and plastic surgery. This functional procedure is typically performed for nasal obstruction caused by septal deviation and may also be performed during aesthetic rhinoplasties or endoscopic sinus surgeries for greater exposure and access. Post-operative pain after septoplasty or septorhinoplasty, is generally mild with more moderate pain reported within the first 24-48 hours after surgery (1,2). Maxillary nerve blocks have been shown to significantly reduce post-operative pain within and analgesic intake during the 24-hour period following endoscopic sinus surgery (3, 4). This randomized, double-blinded, placebo-controlled study will investigate blocks of the pterygopalatine fossa bilaterally using a suprazygomatic approach. It is our hypothesis that this technique will result in decreased post-operative pain, post-operative opioid use, and the morbidity that is associated with it.

4. Background:

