Literature review produced no studies to date on the efficacy of suprazygomatic maxillary nerve blocks for the management of post-operative septorhinoplasty pain control. We currently perform SPG blocks in septorhinoplasty patients based on surgeon and anesthesiology discretion, as well as patients agreement on receiving block, but we currently do not have a standardized way of determining if pain is being controlled in a meaningful way, ie reducing the number the narcotics required post-operatively or reducing the PACU length of stay. Our aim is to conduct a prospective randomized controlled trial using bilateral suprazygomatic maxillary nerve blocks to control post-operative pain in adult patients undergoing septoplasty or septorhinoplasty. We hypothesize that using maxillary nerve blocks in adult patients is a safe and effective way to manage post-operative pain, decreasing complications, post-operative opioid use, and the morbidity that is associated with it.

5. Specific Aims:

The primary aims of this study are to demonstrate in a prospective, randomized, controlled trial, that the application of bilateral suprazygomatic maxillary nerve blockade can safely and effectively:

- 1) decrease the opioid requirement post-operatively

Secondary objectives are to demonstrate

- 1) a decrease in post-anesthesia care unit observation time
- 2) efficiency of SMS based survey for post-operative data collection

6. Research Plan:

PARTICIPANT SELECTION CRITERIA:

The PI and co-investigators already routinely do sphenopalatine ganglion nerve block in our septorhinoplasty patients. All patients undergoing septorhinoplasty who met the inclusion/exclusion criteria (see below) will be offered the opportunity to participate in the study. These patients will initially be approached at their pre-operative surgical visit by the surgical team about their potential interest in participating in the study. If they express interest, consent will be obtained by a surgeon involved in the study during the pre-operative clinic visit. If consent is unable to be obtained by the surgeon prior to surgery, it will be obtained on the day of surgery by a member of the Acute Pain Service to avoid the potential for perceived coercion – that somehow the performance of the operation will be dependent on their participation in the study.

Inclusion criteria shall be as follows:

- 1) Patient presenting for open or endoscopic septorhinoplasty
- 2) Age 18-80

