The group 1 injection procedure will be performed as follows: after preparation of the skin using appropriate skin preparation solution and using aseptic technique, a small-gauge spinal needle will be advanced into the pterygopalatine fossa under ultrasound guidance. Once the needle is properly positioned, 0.5% ropivacaine will be administered at a dose of 20 mg plus 4 mg dexamethasone and the needle will be removed. This procedure will be performed bilaterally.

In group 2 the same procedure will be performed, but the injectate will consist of 5 mL of a balanced crystalloid intravenous solution (4 ml of normal saline) plus 1 mL of 4 mg dexamethasone (each side). This procedure will be performed bilaterally.

Four mL of balanced crystalloid solution plus 1 mL dexamethasone 4mg/mL was chosen as placebo therapy for the control group to aid in blinding since its appearance is identical to ropivacaine plus dexamethasone, to administer the dexamethasone to all patients in the same fashion, and to ensure that effects attributed to the block are a result of the administration of local anesthetic rather than compression neuropraxia from the injection of any material into the pterygopalatine fossa.

Additionally, after induction with general anesthesia, both group 1 and 2 will receive 8 mg of dexamethasone intravenously to reduce PONV and post-operative edema at the surgical site. Dexamethasone when added to nerve blocks has been demonstrated to be neuroprotective, and patients randomized to the placebo arm should also benefit from the neuroprotective effects of the perineural dexamethasone. This is being done in both groups to keep everything as controlled as possible and as mentioned above, to reduce post-operative nausea and vomiting and edema, which would be given regardless of study participation.

Both active treatment and placebo groups will receive bilateral injections of a total volume of 5 mL into the pterygopalatine fossa.

No other changes to the subject's clinical care will be made. All patients will receive the standard of care for pain management for septorhinoplasty, which is 3 days of opioid narcotics (typically oxycodone or hydrocodone) plus over the counter analgesics including acetaminophen and ibuprofen. All opioids will be prescribed as PRN. PACU nursing staff will be informed of patient's participation in the study but will not be informed as to group assignment so that they can remain blinded.

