There will be no procedure note by the anesthesiologist describing the placement of the block. The anesthesiologist will write a note describing the subject's participation in the study with accompanying contact information in the event that the blind must be broken. A sign will also be placed at the head of bed indicating that the subject is a study participant and may have received the bilateral suprazygomatic maxillary nerve blockade with the PIs contact information. Data will be collected including, the time after leaving the operating room to first taking anything by mouth, at what time point did the patient first meet established readiness-for-discharge criteria (return to preoperative baseline oral food/liquid intake AND pain well-controlled with only oral medication) and at what time were they actually discharged. Additionally, information regarding pain scores and analgesic administration, both intraoperative and post-operative, will be gathered from the patient chart for the duration of their admission.

Patients will be sent a survey link via short message service (SMS) to their mobile device on POD 1, 3, and 5. Surveys will be created and distributed to participants using REDCap, a HIPAA compliant and secure platform, and distributed to participants through a third-party system Twilio. For security and privacy concerns, SMS transcriptions do not stay in Twilio's logs and are removed shortly after being completed. Surveys will be composed of 7 questions related to pain at its worst, pain at its least, average pain, current pain, as well as how many narcotic pain pills were consumed within the last 24 hours and what other pain medications were taken, ie acetaminophen, ibuprofen, etc. Relevant questions were adapted from the Brief Pain Inventory (short form) pain assessment. Data will be analyzed using the JMP statistical software package. Each survey will be the exact same set of questions. Patients will be advised to bring their opioid prescription bottle to their post-operative follow up visit and will be asked the same survey of questions during this visit. Additional data will be obtained through patient charting and may include any reported complications, PACU nurse notes, and phone calls to on call providers.

Outcome Measures:

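### After discharge, opioid use is asked about only for the 24 hours before POD 1, 3 and 5 and follow-up, and no tablet count is specified, so total use cannot be computed for the primary aim

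*Combined protocol and SAP*

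**What the plan says.** Section 5 (Specific Aims) lists one primary aim: to "decrease the opioid requirement post-operatively". It gives no time window, unit or summary measure.

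Section 6 (Research Plan, Study Procedures) sets out how the data are obtained:

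- During the admission, pain scores and analgesic administration are taken from the chart.
- After discharge: "Patients will be sent a survey link via short message service (SMS) to their mobile device on POD 1, 3, and 5". The opioid item is "how many narcotic pain pills were consumed within the last 24 hours", and "Each survey will be the exact same set of questions".
- At follow-up: "Patients will be advised to bring their opioid prescription bottle to their post-operative follow up visit", and they "will be asked the same survey of questions during this visit". The day of the visit is not given. Nothing says that tablets are counted, compared with the number dispensed, or analysed.
- Standard pain care is described as "which is 3 days of opioid narcotics (typically oxycodone or hydrocodone" in that section, with over-the-counter analgesics. Opioids are prescribed PRN.

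The Abstract describes pain as "generally mild with more moderate pain reported within the first 24-48 hours after surgery", and the Background says much the same.

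**The concern.** Each survey looks back one day, but the surveys are two days apart. Whatever is taken between one survey and the start of the next look-back is never asked about. The first such gap falls in or next to the period that the protocol itself calls more painful. The one source that could give a complete home total, the bottle, is requested but not put to any stated use.

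The protocol's own rationale is in totals. The Background sets 11 tablets found sufficient in one study against 20-30 typically prescribed, and Possible Benefits hopes for fewer tablets prescribed. A count from three separate days cannot be set beside those figures. It is also a weak basis for the future studies that these preliminary data are meant to support. Use on an unasked day cannot be reliably recovered later.

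**Working it through.** The plan states no figure for coverage, so there is none to reproduce. The check counts hours.

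**Inputs.** Survey days 1, 3 and 5, a 24 h look-back and a 3-day (72 h) supply, all from Study Procedures. Survey clock time relative to surgery is not stated. It enters as an assumed shift *s* in hours, the same for all surveys.

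**Windows.** The survey on day *d* covers hours 24*d* + *s* − 24 to 24*d* + *s*. With *s* = 0 these are 0-24, 48-72 and 96-120.

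- Over five days: 3 × 24 = 72 h, and 72/120 = 60%.
- Over the 3-day supply: 2 × 24 = 48 h, and 48/72 = 67%.
- Gaps: 24-48 h and 72-96 h.

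**Clock time.** The POD 1 window ends at 24 + *s* and the POD 3 window starts at 48 + *s*, so the gap is 24 h whatever *s* is. What changes is where it lies:

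| Shift *s* | Covered of 120 h | Covered of 72 h | First gap | Hours covered within 24-48 |
|---|---|---|---|---|
| −8 | 64 | 40 | 16-40 | 8 |
| −4 | 68 | 44 | 20-44 | 4 |
| 0 | 72 | 48 | 24-48 | 0 |
| +4 | 68 | 44 | 28-52 | 4 |
| +8 | 64 | 40 | 32-56 | 8 |
| +12 | 60 | 36 | 36-60 | 12 |

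If reply times differ between the two days, with shifts *s*₁ and *s*₃, the gap is 24 + *s*₃ − *s*₁ hours. It stays open as long as the two replies are more than 24 h apart.

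**Follow-up visit.** Its look-back adds at most 24 h, wherever the visit falls. The two gaps add up to 48 h, so it cannot close both.

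**Share of tablets, illustration only.** The documents give no daily use, so these patterns for days 1 to 5 are assumed:

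| Assumed pattern | Days 1+3+5 as share of five-day use | Day 2 as share of days 1-3 |
|---|---|---|
| 1-1-1-0-0 | 2/3 = 66.7% | 1/3 = 33% |
| 4-3-2-1-0 | 6/10 = 60% | 3/9 = 33% |
| Falling, ratio 0.6 per day | 1.4896/2.3056 = 64.6% | 0.6/1.96 = 31% |
| Falling, ratio 0.4 per day | 1.1856/1.6496 = 71.9% | 0.4/1.56 = 26% |
| Day-2 peak, 3-4-2-1-0 | 5/10 = 50% | 4/9 = 44% |

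The surveys capture 50-72% of tablets across these patterns, or 60-72% without the day-2 peak. A steeper fall of 75% per day puts 0.25/1.3125 = 19% of three-day use on day 2.

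**What a shift could do.** Suppose control patients take 4-3-2 tablets on days 1 to 3 and block patients 2-5-2. Both total 9. Days 1 and 3 alone give 6 against 4, an apparent saving of 2/6 = 33% where total use is equal. These counts are invented and show only that the surveys could not reveal such a shift.

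**The case against.** The strongest reply is that a cumulative total is one choice of outcome and the plan never commits to it. The primary aim names no window or summary, the Statistical Methods section plans mixed-model repeated-measures ANOVA, which suits sampled time points, and both arms have the same schedule. A randomised comparison on the sampled days is therefore available. That stands: the loss shown is of completeness and sensitivity, and bias is not shown. But a comparison on sampled days speaks for overall requirement only if the effect is similar on the days not sampled, and the plan could not check this.

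Four stronger readings are tempting, and the documents do not support them.

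- A reader might infer that opioid use is never measured. Chart data cover the admission, and the bottle makes a home count possible. What is missing is any instruction to make that count.
- A reader might infer that hours 24-48 are lost entirely. That is exact only when surveys fall at whole multiples of 24 h after surgery; up to 12 of those hours are covered in the range tried, and patients still admitted have chart data. The protocol's phrase is also most naturally read as the first one to two days, and the POD 1 survey covers most or all of the first.
- A reader might infer that the POD 5 opioid item must be near zero because a 3-day supply is used up. Opioids are PRN, so tablets may last longer, and the Background's figures of 11 sufficient and 20-30 prescribed suggest leftovers. The POD 5 survey also carries the pain and non-opioid items.
- A reader might take the capture percentages as estimates for this trial. They rest wholly on assumed patterns.

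The possible overlap of the POD 1 look-back with charted hospital doses is minor. It needs only a rule.

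**Conclusion.** The point holds in this form. Total post-operative opioid use cannot be computed from the data that the plan specifies. The home item nominally covers 72 of 120 h, and 48 of the 72 h of the opioid supply. For common clock-time shifts of −8 to +12 h the ranges are 60-72 h and 36-48 h. A 24 h gap between the POD 1 and POD 3 windows remains at any common clock time, at or near hours 24-48.

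The coverage figures rest on the stated survey days and look-back and on the assumed shifts. They count hours and do not say how many tablets are missed. Because this concerns the sole primary aim and the remedy is cheap, it should be changed for every patient not yet surveyed.

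**What to change.** 1. Reword the pill item to 'since leaving the hospital' on POD 1 and 'since the last survey' on POD 3 and POD 5. Keep the 24-hour item alongside it if daily values are wanted.
2. Record the drug, tablet strength and number dispensed. At the follow-up visit, count the tablets left and record the date.
3. Define the home part of the primary outcome as cumulative use over a stated period, converted to a common opioid unit because patients may receive different drugs. Add it to charted in-hospital use, with a rule that counts no dose twice.
4. Use the bottle count to check the SMS total and to supply the total when surveys are missing. It cannot fill in values for particular days. The check would also inform the secondary objective on SMS data collection.

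A daily survey on POD 1 to 5 with the present 24-hour item would also cover 120 of 120 h, at the price of two more messages per patient.

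The cost is one reworded REDCap item, a few fields on the dispensing and follow-up records, and a minor IRB amendment. The drawbacks are a recall period of 48 h instead of 24 h on POD 3 and POD 5, and a tablet count that assumes missing tablets were taken and depends on patients bringing the bottle.

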The outcome measures for this study will be: decreased post-operative pain, reduced post anesthesia care unit recovery stays, and post-operative opioid use, as well as the morbidity that is associated with it, in patients undergoing septorhinoplasty surgery.

Table of Study Events

Table of Study Events

Activity	Screening	Pre-Op	Intra-Op	Post-Op
Consent	X			
Randomization		X		
Group 1: Suprazygomatic maxillary nerve block			X	
Group 2: Placebo injection with normal saline			X	
Data Collection				X
Data Analysis				X

STATISTICAL METHODS, DATA ANALYSIS, AND INTERPRETATION:

Data will be collected from the patient record regarding the primary and secondary study aims, as well as demographic information including age, sex, height, weight, and BMI on a daily basis for the duration of the hospital admission. Data will be analyzed using ANOVA, ANCOVA and mixed-models repeated-measures ANOVA techniques using the JMP statistical software package from SAS Labs.

Given that these outcomes, to the best of the study team's knowledge, have not been studied previously, no preliminary data exist on which to base power or sample size calculations, and this study is designed to collect such preliminary data on which future studies could be built. That being the case, there is no sample size calculation here. We request permission to enroll 50 patients per group into this study as previous studies involving similar blocks of the maxillary nerve have used group sizes of 20-30.

DATA STORAGE AND DE-IDENTIFICATION PLANS:

Protected health information will be accessed by study team members until data collection is complete, at which point all patients will be de-identified. All retained records will be stored on password-secured data storage devices in accordance with UF policies. Patient contact information stored within REDCap will include participants mobile phone number and medical record numbers. No other patient identifier will be inputted in the REDCap system such as name, date of birth.

7. Possible Discomforts and Risks:

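### Safety is in the primary aim and opioid morbidity is a named outcome, but no described survey question covers side effects and complications are captured passively, so both can at most be described, not demonstrated

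*Combined protocol and SAP*

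**What the plan says.** **Claims.** The primary aim (section 5, Specific Aims) is to demonstrate that "the application of bilateral suprazygomatic maxillary nerve blockade can safely and effectively" reduce the post-operative opioid requirement. No safety endpoint, threshold or margin follows. The hypothesis at the end of section 4 (Background) says that the block "is a safe and effective way to manage post-operative pain, decreasing complications, post-operative opioid use, and the morbidity that is associated with it". The Outcome Measures paragraph in section 6 names opioid use "as well as the morbidity that is associated with it, in patients undergoing septorhinoplasty surgery", with no component, time point or grading for the morbidity.

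**Data collection (section 6, Study Procedures).** "Surveys will be composed of 7 questions related to pain at its worst, pain at its least, average pain, current pain". The two remaining topics described are the opioid tablet count over the previous day and any other analgesics used. The survey goes out on POD 1, 3 and 5, is identical each time, and is asked again at the follow-up visit. On complications the text says: "Additional data will be obtained through patient charting and may include any reported complications"; PACU nurse notes and calls to on-call providers are the other sources named. The anesthesiologist writes no procedure note for the block.

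**Review and analysis.** The Data Safety Monitoring Board paragraph has the PI and lead co-investigators meet at least monthly about adverse events and produce a written report. It gives no event definition, grading or collection form. The statistical section names ANOVA, ANCOVA and mixed-models repeated-measures ANOVA, asks for 50 patients per group, and says that "this study is designed to collect such preliminary data on which future studies could be built".

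**The concern.** A named outcome needs a variable, and opioid morbidity has none. Nausea, vomiting, constipation and drowsiness are not mentioned in any described survey topic. Nor are the block-related risks that section 7 itself lists: infection, bleeding, pressure and facial numbness. Patients are contacted on a schedule after discharge, but on the described content nobody asks them about these events.

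Two things are at stake. The morbidity outcome may end up with almost no post-discharge data, and symptoms not asked about at the time cannot be reliably recovered later. A low or equal count of charted complications could also be read as evidence of safety when it partly reflects how little was asked. Section 8 hopes that the work may change the standard of care, so that misreading would matter.

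**Working it through.** The plan gives no event rate, safety margin, power or sample size calculation, so there is no figure of its own to reproduce. The group size of 50 is supported only by earlier studies that used 20-30 per group.

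**1. What is asked.** Described topics: worst, least, average and current pain (4), opioid pills (1), other pain medicines (1). That makes 6 topics for 7 questions. None of the six concerns a side effect; the seventh is not described.

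**2. What zero events would show if every event were captured.** The exact two-sided 95% upper limit for 0 events in n patients is 1 − 0.025^(1/n).
- One arm: 1 − 0.025^(1/50) = 7.1%.
- Both arms: 1 − 0.025^(1/100) = 3.6%.
- An event with a true rate of 2% would not be seen at all with probability 0.98^50 = 36% in 50 patients, or 0.98^100 = 13% in 100.

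**3. Effect of incomplete capture.** If a fraction c of events reaches the chart, the charted rate is c times the true rate, so the limit on the true rate is the limit above divided by c. The documents give no c; these values are assumptions.

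| c | 0/50 | 0/100 |
|---|---|---|
| 1.00 | 7.1% | 3.6% |
| 0.75 | 9.5% | 4.8% |
| 0.50 | 14.2% | 7.2% |

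**4. Morbidity comparison.** The documents give no control rate, so I assume 10% to 40%, a halving under the block, two-sided 5% alpha and complete capture. Normal-approximation power for two proportions is Φ[(d − 1.96·s0)/s1], where d = p1 − p2, s0 = √(2·p̄(1 − p̄)/n) and s1 = √((p1(1 − p1) + p2(1 − p2))/n). For 20% against 10% with n = 50, s0 = 0.0714 and s1 = 0.0707, so power is Φ[(0.10 − 0.140)/0.0707] = 29%.

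| Control vs block | Power, n = 50 per arm | Power, Fisher exact | n per arm for 80% |
|---|---|---|---|
| 10% vs 5% | 15.5% | 6% | 435 |
| 20% vs 10% | 29% | 20% | 199 |
| 30% vs 15% | 43% | 35% | 121 |
| 40% vs 20% | 59% | 52% | 82 |

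If charts caught half of the events equally in both arms, a true 20% vs 10% would appear as 10% vs 5%, and power would fall from 29% to 15.5%.

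**5. What the arms can separate.** Group 2 has the same bilateral injection, with dexamethasone but no ropivacaine. The between-arm contrast therefore isolates ropivacaine. Harm from the needle is common to both arms and drops out of the contrast, but it can be estimated as an absolute rate over all 100 patients. With no uninjected arm, that rate cannot be split from the effects of surgery.

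**The case against.** The strongest defence is that the study calls itself preliminary, that serious complications would probably surface through PACU notes, phone calls or the monthly review, and that the sham is well justified by blinding, equal dexamethasone and separation of the anesthetic effect from the injection itself. Much of this stands. The monthly review is a real safeguard, but with no stated source it can only look at what passive capture delivers. The preliminary label supports a descriptive aim rather than the wording now used.

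Several stronger readings are tempting and not supported:

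- A reader might infer that lowering opioid morbidity is a numbered aim. It is not; it appears in the hypothesis and in Outcome Measures. Only safety is in the primary aim.
- A reader might infer that the survey has no side-effect item at all. One of the seven questions is not described, so the most that can be said is that none is described.
- A reader might infer that the sham makes a null safety result certain, or safety impossible to study. It does neither. Section 7 lists facial numbness for the active block only, so the arms can differ, and the shared procedure doubles the number of patients in whom needle harms can be counted. The sham has no bearing on whether opioid symptoms are recorded.
- A reader might infer same-day discharge, with almost all events occurring at home. The documents do not state this; they refer to data collected during a hospital admission. How much falls after discharge is unknown.

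**Conclusion.** The point holds in limited form. Safety and opioid-associated morbidity are claimed without a defined endpoint, without a described active question, and without a named analysis for event data. As planned, they can at most be described. The binding limits are passive capture and sample size, not the sham.

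The zero-event limits of 7.1% (50 patients) and 3.6% (100 patients) are best cases that rest on complete capture. The power figures of 15.5% to 59% rest on assumed control rates and an assumed halving; they show that better collection alone would not turn the morbidity comparison into a demonstration. Intravenous dexamethasone in both arms, given partly against nausea and vomiting, may narrow any nausea contrast further.

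This should be corrected, but it does not undermine the randomised comparison of opioid use.

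**What to change.** 1. **Collect.** Add yes/no items on nausea or vomiting, constipation, drowsiness and injection-site problems to the POD 1, 3 and 5 surveys and to the follow-up visit, in both arms. State the recall window; since the previous contact would cover the days that a 24-hour window skips between surveys. Define the first three items, the opioid-related symptoms, as the morbidity outcome. Put any facial numbness item after the pain and pill questions, or only at the visit, to limit unblinding. State what the seventh existing question is, and name these items as a source for the monthly review.
2. **Report.** Give needle-procedure complications pooled over both arms, and ropivacaine-specific effects and opioid symptoms by arm, all with exact 95% confidence intervals and labelled descriptive. Say that similar counts between arms are not evidence that the injection is safe.
3. **Reword.** Change the primary aim from demonstrating a safe and effective reduction to estimating the opioid effect and the complication rate, each with a 95% confidence interval.

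Cost: a few items in the existing REDCap survey, reworded aims and a minor IRB amendment; randomisation and treatment are unchanged. The downsides are a slightly longer survey, a small risk that a numbness question prompts patients to guess their arm, and a more modest safety claim.

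### Chart opioid doses and pain scores stop at discharge, which the block is meant to bring forward, so chart opioid totals partly compare observation time; the home pill counts are not affected in this way but are not joined to them

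*Combined protocol and SAP*

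**What the plan says.** - **Primary aim** (section 5, Specific Aims): to "decrease the opioid requirement post-operatively". No period, unit or summary measure is attached.
- **Chart window** (section 6, Study Procedures): pain scores and analgesic administration "will be gathered from the patient chart for the duration of their admission".
- **Statistical section** (section 6, Statistical Methods, Data Analysis, and Interpretation): "Data will be collected from the patient record regarding the primary and secondary study aims", together with demographics, "on a daily basis for the duration of the hospital admission". The planned methods are ANOVA, ANCOVA and mixed-model repeated-measures ANOVA. No rate, offset, fixed period or adjustment for stay is mentioned.
- **Stay as an outcome**: the first secondary objective is "a decrease in post-anesthesia care unit observation time", and Outcome Measures lists "reduced post anesthesia care unit recovery stays".
- **Discharge readiness** (section 6, Study Procedures): "return to preoperative baseline oral food/liquid intake AND pain well-controlled with only oral medication". The time readiness is first met and the actual discharge time are both recorded.
- **After discharge** (section 6, Study Procedures): "Patients will be sent a survey link via short message service (SMS) to their mobile device on POD 1, 3, and 5". Each survey asks for narcotic pills taken over the preceding 24 hours, with identical questions each time. The same questions are asked at the follow-up visit, to which patients are advised to bring the opioid bottle.

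**The concern.** The chart window closes at an event that comes after randomisation, depends on pain, and is expected to differ between arms. A patient who leaves at 90 minutes contributes 90 minutes of chart doses; a patient kept longer contributes more. At the same hourly need, the shorter stay gives the smaller total, and the difference can be read as opioid sparing. Blinding does not prevent this, because the mechanism is time at risk and not assessor expectation.

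Opioid use and length of stay would then not be two separate pieces of evidence, since part of any fall in the chart total would be the shorter stay counted again.

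Pain scores are affected differently. They do not accumulate, but a shorter stay changes how many scores are taken and how long after surgery. The average per patient is then taken over different periods in the two arms.

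Doses around discharge are also loosely covered. The POD 1 survey has no stated send time. Depending on when it is answered, its 24-hour recall can miss the first hours at home or can include tablets already recorded in the chart.

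**Working it through.** The plan has no sample size or power calculation to reproduce. The only input it supplies is 50 patients per group. Everything else here is an assumption for illustration: control stay 120 min; SD of stay 40 min in both arms (gamma distribution); doses Poisson given the stay; equal opioid need in both arms; two-sided t-test at 0.05. The nominal chance of a false result favouring the block is therefore 2.5%.

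**Constant rate r per hour up to discharge.** For mean stay m hours, the total has mean r·m and variance r·m + r²·(40/60)². With SE = √[(V_control + V_active)/50], the chance of a false result favouring the block is approximately P(Z > 1.96 − difference/SE).

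At r = 1 the control mean is 2.0 and its variance 2.0 + 0.444 = 2.444.

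| Stay shorter by | Active mean | Active variance | SE | Difference/SE | False result favouring block |
|---|---|---|---|---|---|
| 10% | 1.8 | 2.244 | 0.306 | 0.65 | 9.6% |
| 20% | 1.6 | 2.044 | 0.300 | 1.34 | 26.6% |
| 25% | 1.5 | 1.944 | 0.296 | 1.69 | 39.3% |

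Simulation with 20,000 trials agrees: about 9%, 26% and 39%. At 0.5 dose/h it gives about 7%, 16% and 24%. With equal stays it is close to 2.5%. Under a constant rate, the total falls by exactly the percentage by which the stay falls.

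**Rate halving every 30 min.** The expected total for a stay of t minutes is A·(1 − 2^(−t/30)), with A set so that the control mean is again 2 doses. Averaging over the gamma stays gives active means of 1.94, 1.86 and 1.81, which is 3%, 7% and 9% below control. The same formula, with SE about 0.28, gives 4%, 7% and 10%. Most dosing is over before anyone leaves, so the length of stay matters much less.

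**A second model.** This uses 5-MME doses at a mean of 3 MME/h with variation between patients, lognormal stays (CV 0.35), a control stay of 2 h and 4,000 trials. The control total was 6.0 MME; the active total was 5.4, 4.8, 4.2 and 3.6 MME for stays 10%, 20%, 30% and 40% shorter. Two-sided error was 6.6%, 13.9%, 27.3% and 46.4%. With a fixed 6 h window for everyone, both arms averaged about 18.0 MME and error was nominal.

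**How long can a fixed in-hospital window be?** Under the gamma stay model, the share of active patients gone before 60 min is about 9% at a mean stay of 108 min and 24% at 90 min. Sixty minutes cannot be assumed to be a period that nearly all patients complete.

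**The case against.** **The in-hospital total is never named as the primary measure.** This stands. A reader might infer from the statistical section that the primary endpoint is the chart total to discharge. The documents do not support that. The same sentence covers the secondary aims, one of which is the efficiency of the SMS survey, and an admission chart cannot supply that. The Background and Possible Benefits sections also discuss opioid use largely as take-home tablets. The broader gap is that the primary opioid endpoint is undefined. But a chart window is stated, and a chart total computed over it carries this fault.

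**Post-discharge pill counts exist.** This also stands. They are not cut short by discharge, so the bias does not reach all the opioid data. They do not repair the chart total, because they are separate 24-hour snapshots with no stated rule for combining them with chart doses.

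**Equal need with a shorter stay is an awkward scenario.** If stay shortens because pain is better controlled, a lower opioid total is partly real. A block that changed neither pain nor need would not shorten stay by that route, and the error rate would stay nominal. This is a fair criticism of a pure false-positive reading. The likelier harm is a real effect made to look larger than it is.

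**The constant dose rate drives the large figures.** This stands. The plan describes pain after this surgery as generally mild, and a constant rate fits poorly with a readiness criterion of controlled pain. The size has to be given as a range.

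**Pain scores.** A reader might infer that in-hospital mean pain is biased towards the block. That does not follow: longer stays may add later, lower scores, so the bias can go either way.

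**Conclusion.** The point holds for chart-based data. Followed as written, a comparison of chart opioid totals is confounded with length of stay and tends to exaggerate opioid sparing if the active arm's stay is shorter. In-hospital mean pain is not comparable between arms, with no predictable direction. The POD 1, 3 and 5 and follow-up pill counts are free of this particular fault but are not tied to the chart doses, and doses around discharge may be missed or counted twice.

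The direction for opioid totals follows from accumulation over a shorter period. The size does not come from the documents. For stays 10%, 20% and 25% shorter with equal need, false results favouring the block range from about 4%, 7% and 10% to 9%, 26% and 39%, against 2.5%. The upper figures hold only at a constant 1 dose/h up to discharge and should not be read as the trial's expected error rate. Nor do the documents support concluding that the opioid aim as a whole is invalid. The change is worth making because it is cheap and uses mostly data already planned.

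**What to change.** 1. **One opioid total over one period.** For every patient, count from injection (or leaving the operating room) to 24 h: chart doses up to discharge plus home doses after it, in a common opioid-equivalent unit. State the rule that joins the two sources.
2. **POD 1 survey.** Send it at a fixed time about 24 h after surgery, and add or reword one item to ask for narcotic pills taken since leaving the hospital. Amend the Study Procedures statement that every survey is identical.
3. **In-hospital pain.** Compare scores at fixed times after PACU arrival, within a period chosen from local stay data so that nearly all patients complete it.
4. **Whole-stay chart totals.** Report them as descriptive only, beside length of stay.
5. **Timestamps.** Discharge time is already collected; add the injection time.

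The cost is some protocol wording, one timestamp, one survey item and a scheduled send time. The 24 h total will depend on POD 1 survey response, and late in-hospital scores will drop out of the in-hospital pain comparison.
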